### **Microbiological Determinations**

We will record the results of all blood cultures that are obtained within 72 hours before the first dose of study drug and up to 72 hours after the last dose of study drug. If CSF or urine (obtained by catheterization or suprapubic tap) is collected as part of the sepsis work-up, these results will be recorded on the CRF.

Special instructions for the collection, labeling, preparation, handling, and storage of specimens will be clearly detailed in the Manual of Procedures (MOP).

## 7 STUDY PRODUCT DESCRIPTION

### 7.1 Dosage and Study Drug Information

#### 7.1.1 Rationale for Dose Selection

**Rifampin:** Infants receiving rifampin 5–10 mg/kg/day demonstrate wide inter-patient variability in rifampin concentrations, with some patients demonstrating low peak and trough plasma concentrations. A higher dose might provide higher therapeutic exposure without adverse effects. In addition, high inter-patient variability may lead to the need for rifampin therapeutic drug monitoring.

Record all doses of Rifampin, Ticarcillin-clavulante, or Clindamycin for up to 6 SOC doses prior to and including the first on-study dose after the informed consent is signed and any subsequent SOC doses through last dose. The last dose of study drug dosing is defined as the fourth dose for rifampin, and the sixth dose of clindamycin or ticarcillin-clavulanate after enrollment, even if the clinicians continue the study drug.

**Table 5.** Rifampin Dosing

Cohort	GA	PNA	Dose
1	<32 weeks	<14 days	10 mg/kg Q 24 hours x 4 doses
2	<32 weeks	≥14 days–120 days	15 mg/kg Q 24 hours x 4 doses
3	≥32 weeks	<14 days	15 mg/kg Q 24 hours x 4 doses
4	≥32 weeks	≥14 days–120 days	20 mg/kg Q 24 hours x 4 doses

**Ticarcillin-clavulanate** (based on ticarcillin component): Older infants receiving ticarcillin-clavulanate 50–100 mg (based on ticarcillin component) every 8 hours demonstrated wide variability in ticarcillin concentrations, with some patients demonstrating low peak and trough plasma concentrations. Premature infants will likely need a longer interval because of a lower CL.

**Table 6.** Ticarcillin Dosing

Cohort	GA	PNA	Dose
1	<30 weeks	<14 days	75 mg/kg Q12 hours x 6 doses
2	<30 weeks	≥14 days–45 days	75 mg/kg Q 8 hours x 6 doses
3	<30 weeks	>45 days–90 days	75 mg/kg Q 6 hours x 6 doses

All dosing regimens are similar to alternative published regimens.

**Clindamycin:** In adults, clindamycin is extensively metabolized by the liver cytochrome P450 system and subsequently eliminated by the kidneys. Clindamycin inhibits cytochrome P450 2C9, which suggests this enzyme may be responsible for its metabolism. In a clindamycin PK study of newborns, term infants during the first 3 days of life had reduced clindamycin elimination with a weight-adjusted CL that was approximately one quarter of adult CL and an elimination half-life 3 times that of the adult value. Infants born at 28–30 weeks gestation had further reduced CL to a third of that seen in term infants, with an associated half-life 3 times longer than term infants. This large difference between term and preterm infants suggests rapid maturation of clindamycin elimination pathways. Thus, we propose to decrease the dosing interval.

**Table 7.** Clindamycin Dosing

Cohort	GA	PNA	Dose
1	<30 weeks	<14 days	10 mg/kg Q 12 hours x 6 doses
2	<30 weeks	≥14 days–45 days	10 mg/kg Q 8 hours x 6 doses
3	<30 weeks	>45 days–120 days	10 mg/kg Q 6 hours x 6 doses

#### **7.1.2 Rifampin, ticarcillin-clavulanate, and clindamycin local standard of care dosing**

If the site Principal Investigator deems it appropriate for the infant to receive the local standard of care dose, this SOC dose may be selected and administered as the study dose throughout the on-study dosing period.

#### **7.1.3 Formulation, Packaging, and Labeling**

All study drugs will be standard intravenous formulations. This protocol will not specify the brand of product. Each product will be “off the shelf” as determined by the site. Detailed information will be part of the MOP.

#### **7.1.4 Product Storage and Stability**

Detailed information will be part of the MOP.

#### **7.1.5 Preparation and Administration of Study Intervention/Investigational Product**

The pharmacist at each site will prepare and dispense the study drug. IV study drug will be dispensed by the pharmacy in appropriately sized syringes. If the infant receives study drug as part of clinical care, the dose and frequency will be recorded.

Detailed information will be part of the MOP.

## 7.2 Concomitant Medications/Treatments

All drugs and/or treatments are permitted while on study and will be recorded on the CRF.

## 8 ASSESSMENT OF SAFETY

### 8.1 Methods and Timing for Assessing, Recording, and Analyzing Safety Parameters

Safety will be assessed from the time of informed consent through 72 hours after last study dose (adverse events) and 7 days after last study dose (serious adverse events, serious suspected adverse reactions, serious adverse reactions, suspected adverse reaction, adverse reactions). The last dose of study drug dosing is defined as the 4th dose of rifampin and the 6th dose of clindamycin or ticarcillin-clavulanate after enrollment, even if the clinicians continue the study drug. Safety will be assessed by frequency and incidence of adverse events (AEs) and serious AEs (SAEs). The BPCA data monitoring committee (DMC) convened by NICHD will review data and safety information from study participants on a quarterly basis.

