## 6.5 Final Study Visit

### Follow-up Assessment (Day 11)

For 7 days following the last dose of study drug, participants will be followed for the development of adverse reactions. These will be recorded on the CRF.

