#### 8.1.1 Adverse Events

An **adverse event** is any untoward medical occurrence in humans, whether or not considered drug-related, that occurs during the conduct of a clinical trial. Any change in clinical status (routine labs, physical examinations, etc.) that is considered clinically significant by the study investigator is considered an AE.

**Suspected adverse reaction** is any adverse event for which there is a reasonable possibility that the drug caused the adverse event. A reasonable possibility implies that there is evidence to suggest that the drug caused the event.

**Adverse reaction** is any adverse event caused by the drug.

A **serious adverse event** or **serious suspected adverse reaction** or **serious adverse reaction** as determined by the investigator or the IND sponsor is any event that results in any of the following outcomes:

1. Death
2. Life-threatening AE (life-threatening means that the study participant was, in the opinion of the investigator or IND sponsor, at immediate risk of death from the reaction as it occurred and required immediate intervention)
3. Persistent or significant incapacity or substantial disruption of the ability to conduct normal life functions
4. Inpatient hospitalization or prolongation of existing hospitalization
5. Important medical event that may not result in 1 of the above outcomes but may jeopardize the health of the study participant or require medical or surgical intervention to prevent 1 of the outcomes listed in the above definition of serious event

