#### **Follow-up of AEs**

Reportable events that are identified at the last assessment (or the early termination visit) must be recorded on the AE CRF with the status of the AE noted and followed until resolution. All serious suspected adverse reactions will be followed until resolution. All other events that cannot be resolved by 30 days after last study contact will be considered resolved by convention and entered in the electronic data capture (EDC) system as such. Any event beginning more than 7 days after the last dose of study drug will not be captured.

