## 8.2 Guidelines for Determining Causality

The investigator will use the following question when assessing causality of an adverse event to study drug where an affirmative answer designates the event as a suspected adverse reaction: Is there a reasonable possibility that the drug caused the event? “Reasonable possibility” means there is evidence to suggest a causal relationship between the drug and the adverse event.

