### **Safety and Clinical Laboratory Analyses**

The number of AEs, suspected adverse reactions, and adverse reactions will be summarized overall, by severity, and by each Medical Dictionary for Regulatory Activities (MedDRA) system organ class and preferred term. Prior and concomitant medications will be summarized by World Health Organization (WHO) drug class. Laboratory data, such as hematology and serum chemistry data, will be tabulated by GA and PNA group. Summary statistics for changes from baseline will be presented. Continuous laboratory measurements will be described at each visit using univariable descriptive statistics (mean, median, etc.); observed values and changes from baseline will be summarized. Lab tests reflective of liver toxicity (e.g., ALT, AST) will be further summarized in terms of the most extreme values and largest changes from baseline (in the appropriate direction) observed from start of study drug through the end of therapy.

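### Adverse events are collected to 72 hours but drug-attributed events to 7 days, so the counts that section 10.3 summarises together cover unequal windows and cannot be read against each other

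*Protocol*

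**What the plan says.** Protocol section 8.1 starts safety assessment at informed consent and runs it "through 72 hours after last study dose (adverse events) and 7 days after last study dose". The 7-day category is listed as "serious adverse events, serious suspected adverse reactions, serious adverse reactions, suspected adverse reaction, adverse reactions". Section 6.5 is consistent with that: "For 7 days following the last dose of study drug, participants will be followed for the development of adverse reactions".

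Section 8.1.1 nests the categories. A suspected adverse reaction "is any adverse event for which there is a reasonable possibility that the drug caused the adverse event", and an adverse reaction is likewise an adverse event, one caused by the drug. Attribution rests with the investigator. Section 8.2 begins: "The investigator will use the following question when assessing causality of an adverse event to study drug", and a single yes/no question follows. Section 4 describes the study as open-label and not randomised.

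On analysis, section 10.3 (Safety and Clinical Laboratory Analyses) says: "The number of AEs, suspected adverse reactions, and adverse reactions will be summarized overall, by severity", and by MedDRA class and term. It gives no cut-off for these counts.

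Other places describe the period differently. Table 4 (section 6.1) marks adverse events across the post-therapy column to day 9/11 without restriction. The follow-up text under section 8.1.3 sets only an outer limit: "Any event beginning more than 7 days after the last dose of study drug will not be captured". Section 4 speaks of up to 30 days of safety monitoring.

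**The concern.** The longer period for serious events is not the difficulty, because they enter whatever their cause. The difficulty lies with non-serious events. From 72 hours to 7 days, whether such an event belongs in the database under section 8.1 depends on the investigator's causality judgement, and that judgement is itself one of the reported results.

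There is no control group, so a reader will naturally set the number of reactions beside the number of adverse events to judge how much is attributed to the drug. The two numbers do not describe the same period. The size of the mismatch also varies with the dosing regimen, so no single factor corrects it.

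Sections 7.1.1 and 8.1 fix the last study dose as the fourth (rifampin) or sixth (the other two drugs), whether or not clinicians carry on with the drug. For infants who continue, the interval in which non-serious events are filtered by attribution may still be time on drug.

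**Working it through.** The protocol gives no adverse event rate and no related share, so there is no figure of its own to reproduce. The check has three parts.

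**1. What qualifies when (section 8.1 read with 8.1.1)**

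| Event | Consent to 72 h after last dose | 72 h to 7 days |
|---|---|---|
| Serious, any cause | yes | yes |
| Non-serious, attributed to drug | yes | yes |
| Non-serious, not attributed | yes | no |

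Only the last row changes, and only attribution separates it from the row above.

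**2. Length of the windows**

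Inputs: number of doses n and interval τ from the dosing tables in section 7.1.1; 72 h and 7 days (168 h) from section 8.1. From first dose:

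- adverse event window A = (n − 1)τ + 72
- reaction and serious event window B = (n − 1)τ + 168
- difference B − A = 96 h; relative excess 96/A

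| Regimen | First to last dose | A | B | 96/A |
|---|---|---|---|---|
| q24h × 4 (rifampin) | 3 × 24 = 72 h | 144 h | 240 h | 67% |
| q12h × 6 | 5 × 12 = 60 h | 132 h | 228 h | 73% |
| q8h × 6 | 5 × 8 = 40 h | 112 h | 208 h | 86% |
| q6h × 6 | 5 × 6 = 30 h | 102 h | 198 h | 94% |

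Section 8.1 starts the clock at consent, so these percentages are upper values. Table 4 allows screening from 72 h before day 0. If consent came a full 72 h before the first dose, the excess would be 96/(144 + 72) = 44% for rifampin and 96/(102 + 72) = 55% for q6h. Standard-of-care dosing, allowed by section 7.1.2, could also alter the intervals.

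**3. Illustration of the effect on a related share**

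Assumptions, none from the protocol: constant event rates from first dose; true related share p = 10% over the full 7-day period; a fraction s of unrelated events is serious, varied from 0 to 50%. Late reactions are counted as adverse events, as section 8.1.1 requires, and late unrelated serious events are included:

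recorded share = pB / [pB + (1 − p)((1 − s)A + sB)]

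- Rifampin, s = 0: 24 / (24 + 0.9 × 144) = 24/153.6 = 15.6%
- Rifampin, s = 50%: 24 / (24 + 0.9 × 192) = 24/196.8 = 12.2%
- q6h, s = 0: 19.8 / (19.8 + 0.9 × 102) = 19.8/111.6 = 17.7%
- q6h, s = 50%: 19.8 / (19.8 + 0.9 × 150) = 19.8/154.8 = 12.8%

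The q12h and q8h regimens fall between these (12.3–16.1% and 12.6–17.1%). With one window for all categories, A and B are replaced by the same length and the formula returns p, so 10% stays 10%.

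**The case against.** The strongest reply is that the protocol plans counts. It names no ratio of reactions to adverse events, and the analysis window of a safety table is ordinarily a matter for the statistical analysis plan. Onset date and causality are recorded for each event (section 8.1.3), so a common-window table can be produced without changing data collection. This is right about the ratio and about how easily the table can be made. It does not remove the point, because the protocol itself fixes the unequal collection rule and then says the categories will be summarised together. That is more than an omitted detail.

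A reader might infer several stronger things that the documents do not support:

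- **That a reported share would be 17–19%.** This divides 7-day reactions by 72-hour adverse events (10% × 1.67 to 10% × 1.94, or 16.7–19.4%). It leaves late reactions out of the set to which section 8.1.1 assigns them. Counted properly, the worst case is 15.6–17.7%, and it is lower once late unrelated serious events enter.
- **That inflation is guaranteed.** Against full 7-day capture the recorded share cannot be lower than the true one. Against a uniform 72-hour share it can be. For rifampin with p = 10%, s = 10%, and all related events starting by 72 h after the last dose, the recorded share is 0.1/(0.1 + 0.9 × (0.9 × 144/240 + 0.1)) = 14.8%. The uniform 72-hour share is 0.1/(0.1 + 0.9 × 144/240) = 15.6%.
- **That reactions could outnumber adverse events.** This needs an adverse event row cut strictly at 72 h, and section 10.3 specifies no such row.
- **That late unrelated non-serious events are certainly lost.** Table 4 and the outer limit under section 8.1.3 point the other way. They do not cancel section 8.1, but they leave it unclear what sites will record.

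**Conclusion.** The point holds as an inconsistency between collection and tabulation. Under section 8.1 the reaction counts cover 96 hours more than the adverse event counts, and in that interval a non-serious event qualifies only by attribution. From first dose the excess is about 67–94%, less from consent. The counts in section 10.3 should therefore not be read against each other as planned.

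The figure of about 12–18% for a true 10% is an illustration only. It rests on constant rates and an assumed serious fraction of 0–50%, and it is relative to full 7-day capture.

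The consequence is minor. Safety is a secondary, descriptive outcome, and the laboratory summaries are separate from these counts. Serious events have one 7-day window whatever their cause, and the halting rule in section 8.4 uses only serious attributed events, so neither is affected.

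**What to change.** In section 10.3, state that adverse events, suspected adverse reactions and adverse reactions are tabulated over one common window, from consent to 72 hours after the last study dose. List serious events and attributed events with onset from 72 hours to 7 days in a separate table, outside those counts.

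Also reconcile the adverse event collection period across section 4, Table 4, section 6.5, section 8.1 and the follow-up text under section 8.1.3, so that sites record the same events after 72 hours.

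The tabulation takes a sentence or two and no new data. The cost is slightly lower headline reaction counts, with the later reactions still shown in their own table. The common window makes the counts comparable, but it does not recover late unrelated non-serious events that sites did not record. A comparable 7-day table would be possible only if the reconciled rule collects all adverse events to 7 days.

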#### 8.1.1 Adverse Events

An **adverse event** is any untoward medical occurrence in humans, whether or not considered drug-related, that occurs during the conduct of a clinical trial. Any change in clinical status (routine labs, physical examinations, etc.) that is considered clinically significant by the study investigator is considered an AE.

**Suspected adverse reaction** is any adverse event for which there is a reasonable possibility that the drug caused the adverse event. A reasonable possibility implies that there is evidence to suggest that the drug caused the event.

**Adverse reaction** is any adverse event caused by the drug.

A **serious adverse event** or **serious suspected adverse reaction** or **serious adverse reaction** as determined by the investigator or the IND sponsor is any event that results in any of the following outcomes:

1. Death
2. Life-threatening AE (life-threatening means that the study participant was, in the opinion of the investigator or IND sponsor, at immediate risk of death from the reaction as it occurred and required immediate intervention)
3. Persistent or significant incapacity or substantial disruption of the ability to conduct normal life functions
4. Inpatient hospitalization or prolongation of existing hospitalization
5. Important medical event that may not result in 1 of the above outcomes but may jeopardize the health of the study participant or require medical or surgical intervention to prevent 1 of the outcomes listed in the above definition of serious event

#### Guidelines for Assessing Severity of an Adverse Event

The investigator should use the following definitions when assessing intensity of an adverse event:

1. MILD: Participant is aware of symptoms or has minor findings, but tolerates them well and no or minimal intervention required
2. MODERATE: Participant experiences enough symptoms or findings to require intervention
3. SEVERE: Participant experiences symptoms or findings that require significant intervention

#### **8.1.2 Unexpected Adverse Event Definition**

Any AE, the specificity or severity of which is not consistent with the package insert or investigational brochure.

#### **8.1.3 Identification of Events and Timeframe for Reporting**

As all participants in this study will have pre-existing medical conditions and will be currently hospitalized, those pre-existing conditions will not be considered as adverse events. New events that occur or worsening through frequency or intensity of pre-existing conditions will be reported as adverse events. All reportable events as defined above, determined to be an AE based on physical examination, laboratory findings, or other means, will be recorded in the source documents and entered in the electronic CRF (eCRF). Each event will be recorded on an AE case report form starting after consent has been obtained. The investigator will provide date of onset and resolution, severity, action(s) taken, changes in study drug dosing, causality to study drug, and outcome.

#### **Follow-up of AEs**

Reportable events that are identified at the last assessment (or the early termination visit) must be recorded on the AE CRF with the status of the AE noted and followed until resolution. All serious suspected adverse reactions will be followed until resolution. All other events that cannot be resolved by 30 days after last study contact will be considered resolved by convention and entered in the electronic data capture (EDC) system as such. Any event beginning more than 7 days after the last dose of study drug will not be captured.

#### **8.1.4 Interim Safety Analysis**

**Rifampin:** The study team will evaluate safety after 3 participants are enrolled in each cohort and receive the protocol dose. The safety review will be performed within 1 week after all data on the third participant in each cohort are entered and there are no pending queries. Enrollment in the cohort will be halted if there are any safety concerns.

**Clindamycin:** The study team will evaluate safety after 3 participants ≤26 weeks gestation are enrolled in cohort 1. The safety review will be performed within 1 week after all data on the third participant ≤26 weeks gestation in cohort 1 are entered and there are no pending queries. Enrollment for infants ≤26 weeks gestation in cohort 1 will be halted if there are any safety concerns. During the safety review, enrollment in this cohort will continue except for infants ≤26 weeks gestational age at birth.

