Published data on the safety and PK of clindamycin in preterm and term infants are extremely limited (Table 3). In a study evaluating the PK of 20 mg/kg/day of clindamycin divided q 6–8 hours in term and preterm infants, CL was directly related to PNA. The half-life of clindamycin was 8.7 hours for infants <28 days of age and 3.6 hours for infants >4 weeks of life. Serum half-life in adults and older children are 3.0 and 2.5 hours, respectively. CL was not presented by body weight but was found to be 1.92 L/hr for infants >3.5 kg and 0.31 L/hr for infants <3.5 kg. However, no infant in this study was <28 weeks gestation at birth, and only 1 infant was <1000 g birth weight. Only 2 term infants <14 days of age were enrolled in the study. Drug

accumulation was observed in the 1 infant <1000 g who was administered 15 mg/kg/day every 8 hours. No safety data were collected in this study. In a second study of 12 infants, no correlation between clindamycin CL and renal function, PNA, GA, or postmenstrual age was observed. However, the assay used in this study could not distinguish between clindamycin or its metabolites. CL ranged from 37.8 to 135 mL/kg/hr. Again, no safety data were presented.

**Table 3.** Previous PK Studies of IV Clindamycin in Infants

Reference	Term Infants	Preterm Infants	Dose	Route	Age
1984 	5	0	5 mg/kg q6h	IV	2–27 days PNA
	0	16	6.67 mg/kg q8h	IV	28–40 weeks GA
	0	3	5 mg/kg q8h	IV	28–40 weeks GA
	19	0	5 mg/kg q6h	IV	4–51 weeks PNA
1986 	2	10	3.15–11 mg/kg q6h	IV	26–39 weeks GA

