2. GA/PNA
  - i. Rifampin: <121 days PNA
  - ii. Ticarcillin-clavulanate: <91 days PNA AND <30 weeks GA
  - iii. Clindamycin: <121 days PNA AND <30 weeks GA
3. Sufficient intravascular access
4. Suspected systemic infection

OR

Receiving 1 of the study drugs per local standard of care

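### The clindamycin interim safety review for infants ≤26 weeks counts enrolled infants whatever their dose, so it may include fewer than 3 at 20 mg/kg/day or more, and nothing requires a repeat.

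*Protocol*

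**What the plan says.** Protocol 8.1.4 (Interim Safety Analysis) sets two triggers in adjacent paragraphs. For rifampin: "The study team will evaluate safety after 3 participants are enrolled in each cohort and receive the protocol dose". For clindamycin: "The study team will evaluate safety after 3 participants ≤26 weeks gestation are enrolled in cohort 1". The clindamycin review follows within a week of complete, query-free data on the third such infant. While it runs, cohort 1 stays open except to infants ≤26 weeks, and enrolment of that group stops if a safety concern is found. Nothing in 8.1.4 calls for a second review.

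Table 7 (section 7.1.1) gives the cohort 1 regimen as "10 mg/kg Q 12 hours x 6 doses". Section 7.1.2 applies to all three drugs and allows an alternative: where the site investigator judges the local standard-of-care dose appropriate, "this SOC dose may be selected and administered as the study dose throughout the on-study dosing period". Section 5.2 also offers an entry route for infants already treated: "Receiving 1 of the study drugs per local standard of care". Section 7.1.5 adds: "If the infant receives study drug as part of clinical care, the dose and frequency will be recorded".

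**The concern.** The review exists because infants ≤26 weeks are the least studied clindamycin group. Of the 1984 infant study, Protocol 2.1 says that "no infant in this study was <28 weeks gestation at birth" and that "accumulation was observed in the 1 infant <1000 g who was administered 15 mg/kg/day every 8 hours". It adds that neither infant clindamycin study in Table 3 provided safety data. The review is therefore the first planned look at safety in this group.

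If some of the infants reviewed were on a local dose below 20 mg/kg/day, a clean result says less about the cohort 1 dose than a count of 3 suggests. Enrolment could then resume at the full dose with no planned second look. The rifampin paragraph closes this route by requiring receipt of the protocol dose; the clindamycin paragraph leaves it open.

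**Working it through.** The trigger of 3 is a fixed count with no formula behind it, so the protocol has no figure here to reproduce.

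**1. The two triggers compared (8.1.4).**
- Rifampin: 3 per cohort, enrolled and given the protocol dose.
- Clindamycin: 3 infants ≤26 weeks, enrolled in cohort 1, at any dose.

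With 7.1.2 in force, the number of those 3 who received at least the cohort 1 daily dose can be 0, 1, 2 or 3.

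**2. Daily doses.**
- Cohort 1 (Table 7): 10 × 2 = 20 mg/kg/day.
- 1984 study (Table 3): 16 preterm infants at 6.67 × 3 = 20 mg/kg/day; 5 + 19 = 24 term infants at 5 × 4 = 20 mg/kg/day; 3 preterm infants at 5 × 3 = 15 mg/kg/day.
- 1986 study (Table 3): 3.15 × 4 = 12.6 up to 11 × 4 = 44 mg/kg/day.

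Past regimens thus lie below, at and above 20 mg/kg/day. They do not show what the sites in this trial use.

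**3. Chance of a shortfall.** The protocol gives no local doses or shares. Assume that a share s of infants ≤26 weeks receives less than 20 mg/kg/day, independently between infants, and that exactly 3 are reviewed. Then P(fewer than 3 at 20 mg/kg/day or more) = 1-(1-s)^3.

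| s (assumed) | (1-s)^3 | Chance of shortfall |
|---|---|---|
| 5% | 0.857 | 14% |
| 15% | 0.614 | 39% |
| 25% | 0.422 | 58% |

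**4. If 4 infants are reviewed.** The pause begins with the review, after clean data on the third infant, so a fourth infant could enrol first. If that infant is included, the shortfall chance is 1-[(1-s)^4 + 4s(1-s)^3]:
- s = 5%: 1-(0.8145 + 0.1715) = 1%.
- s = 15%: 1-(0.5220 + 0.3685) = 11%.
- s = 25%: 1-(0.3164 + 0.4219) = 26%.

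**5. What a shortfall costs.** Suppose a true event rate of 20% at the cohort 1 dose (an assumption). The chance of seeing at least one event among infants at that dose is 1-0.8^3 = 49% with 3 infants, 1-0.8^2 = 36% with 2, 20% with 1 and zero with none.

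**The case against.** The strongest reply is that the difference between the drugs is deliberate. Rifampin is planned at 10–20 mg/kg, against 5–10 mg/kg in the 2006 neonatal study (Tables 1 and 5), so dose is the new element and every cohort is reviewed. For clindamycin only the ≤26-week group is singled out, so gestation is the new element. This may well be the intention. It supports keeping the existing trigger, but it does not make a review at lower doses equivalent to one at 20 mg/kg/day.

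Other protections also continue: the halt at serious reactions in 2 or more participants on a drug (8.4), medical monitor review of each serious event (8.3.1, 8.5), quarterly committee review (8.5) and an interim PK analysis in the same infants (10.3). If clearance is roughly independent of dose (an assumption), an infant on a lower dose still informs expected exposure at 20 mg/kg/day. Doses are recorded, so the study team could take them into account unprompted. All this stands and keeps the point small. None of it, however, requires 3 infants ≤26 weeks at this dose.

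Three stronger readings are tempting and not supported:
- **Local doses are likely to be lower, as the 15 mg/kg/day example suggests.** That regimen was given to 3 of the 43 infants listed for the 1984 study; the other 40 received 20 mg/kg/day. The documents say nothing about local practice at the sites.
- **Any departure from the Table 7 regimen weakens the review.** An equal daily dose leaves no clear gap, and a tolerated higher dose is still informative. Only lower daily doses count as a shortfall here.
- **The accumulation in one small infant shows harm.** Protocol 2.1 says that study collected no safety data, so the observation shows that exposure matters, not that toxicity occurred.

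**Conclusion.** The point holds as a minor one. The clindamycin trigger sets no dose condition, local dosing is allowed, and no repeat is required, so the review may rest on fewer than 3 infants ≤26 weeks at 20 mg/kg/day or more. These three facts come from the text.

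The size does not. The 14%, 39% and 58% rest on assumed shares of 5%, 15% and 25%, on independence between infants and on exactly 3 being reviewed. Sites often share one dosing practice, so independence is doubtful. If no site uses a lower dose, the gap is zero. A review of 3 infants is a weak screen even at full dose, so the gain from closing the gap is limited. It is worth having because it costs so little.

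**What to change.** Keep the existing review and its pause during the review. Add to 8.1.4 (Clindamycin):

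> The review will report the clindamycin dose each infant received. If fewer than 3 of the infants ≤26 weeks reviewed received a total daily dose of at least 20 mg/kg/day, the review will be repeated once 3 such infants in cohort 1 have received it.

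Stating the threshold as a daily dose settles whether a regimen such as 6.67 mg/kg every 8 hours counts (it does). It also avoids repeats prompted only by equal or higher doses. For illustration, suppose 10%, 30% or 50% of infants departed from the Table 7 regimen and half of those departures were lower. Requiring the exact regimen would then force a repeat in 1-0.9^3 = 27%, 1-0.7^3 = 66% or 1-0.5^3 = 88% of cases, against 14%, 39% or 58% under the wording above.

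**Cost.** No new data are needed, because doses are already recorded (7.1.1, 7.1.5). The first review is not delayed. There may be one further short review and pause for infants ≤26 weeks, only when lower doses were given. Reaching 3 at the dose takes on average 3/(1-s)-3 = 0.16, 0.53 or 1.0 infants beyond the first 3 at s = 5%, 15% or 25%.

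The repeat may not be reached if few such infants enrol. If only 4 enrol in all (an assumption) and the first 3 fell short, it is reached with probability 3s(1-s)^3 / [1-(1-s)^3]: 0.129/0.143 = 90%, 0.276/0.386 = 72% and 0.316/0.578 = 55%. Even then, the reported doses would show what the first review covered.
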